A single cohort of patients will be used for all 3 Aims (i.e. both intervention and control groups recruited into the randomized controlled trial (RCT) will form a single cohort for analyses in Aims 2 and 3). We will enroll 54 patients from all Johns Hopkins Hospital adult ICUs. If patients are lost to follow-up, we will enroll up to 10 additional patients to obtain 12-week outcomes assessments on a total of 54 patients (27 in each group). Oral informed consent will be obtained from all participants.

Aim 1 Methods: We will conduct a single-site, pilot RCT (N=54) evaluating the feasibility (primary objective) and efficacy (secondary objective) of a 12-week behavioral activation-rehabilitation (BA-R) intervention versus “usual care”, in acute respiratory failure (ARF) survivors. We will evaluate the BA-R intervention via an RCT study design, with blinded outcome assessments. We will test the feasibility of this intervention (primary outcome) and its efficacy (secondary outcome) at the end of intervention. Figure 2 shows study timeline.

[figure not shown]
After return home, consented patients will be randomized to: (1) behavioral activation and rehabilitation (BA-R) intervention or usual care. Randomization will occur via web-based tool, using variable-sized

blocks from 2 to 4, and stratified by history of depression prior to ICU admission (based on chart review and patient interview). Baseline variables are detailed in Table 1 below.

Table 1: Baseline Variables

Variable	Collection	Measurement Scale
Patient Variables		
Age/sex/race	Chart review	Continuous/Binary/Categorical
Education (number of years/highest attainment)	Patient interview	Continuous/Categorical
Employment & Health Insurance status	Patient interview	Categorical
Comorbidity indices: Charlson (CCI) ^a & Functional (FCI) ^b	Chart review	Ordinal
Alcohol intake/misuse / Drug abuse	Chart review	Categorical
Physical function at baseline: AMPAC-CAT ^{87,88 c}	Patient interview	Continuous
ICU and Hospital Variables		
ICU admission diagnosis (e.g., sepsis, renal failure)	Chart review	Categorical
Severity of illness: APACHE II ^d	Chart review	Continuous
Benzodiazepine use and dosing ^{56,89,90}	Chart review	Continuous
Daily ICU Sedation Status: RASS ⁹¹	Chart review	Ordinal
Daily ICU Delirium Status: CAM-ICU ^{92,93}	Chart review	Categorical
Daily Minimum Glucose ⁹⁰	Chart review	Continuous
ICU and Hospital Length of Stay	Chart review	Continuous

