c. Statistical plan including sample size justification and interim data analysis.

Sample Size: As a pilot RCT, we aim to enroll a convenience sample of ~1.5 patients/month, for a total of 54 patients (based on 36 months of recruitment; see Timeline-Candidate Statement). Extensive experience enrolling ARF patients in prior studies by our group^{10,121,125-127} suggests this rate is feasible for a K-23 award at this study site. We expect an overall <15% missing completion rate due to mortality and loss to follow-up (in our prior study of >500 ARF survivors, loss to follow-up was 2% with 7% mortality at 6 months¹²⁵), thus, we expect 54 patients to complete the intervention. With 54 participants (27 in each group), assuming 5% alpha, 80% power and HAD SD of 4.2 points based on our prior research in ARF survivors^{89,90}, for our secondary aim of efficacy, we can detect a 3.1 point difference in HADS score between the 2 treatment groups, which approximates HAD's 2.9 point minimum important difference (MID) in ARF survivors.¹²⁸ This proposed enrollment rate and sample size is consistent with existing pilot/feasibility trials in ARF research.^{101,129,130}

Statistical Analysis

Hypothesis 1a: *A 12-week BA-R intervention in ARF survivors will be feasible, as demonstrated by an average accrual rate of 1.5 patients per month, completion of ≥80% of the intervention phone calls, and ≤15% of enrolled patients lost to follow-up for outcomes assessments at end of the 12-week intervention.* We will assess the total number of intervention phone calls completed per patient as a proportion of the number of intervention phone calls each patient is intended to complete (i.e., 9 intervention calls – weekly during first 6 weeks and bi-weekly for second 6 weeks of the 12-week protocol). We also will assess total number of intervention phone calls completed by all study participants as a proportion of total intervention phone calls expected in the study. We will calculate the number of patients completing the 12-month follow-up session as a proportion of the number of patients enrolled to measure loss to follow-up.

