Hypothesis 1b: *At the end of the 12-week BA-R intervention, ARF survivors in the BA-R versus “usual care” group will demonstrate decreased depressive symptoms, less impairments in physical function and quality of life, and reduced healthcare utilization.* Analyses will follow a modified intention-to-treat principle and a 2-tailed p<0.05 is statistically significant. Patient mortality is expected to occur infrequently (see Sample Size above) and not to differ by treatment vs. control group; therefore, all analyses will be conducted for 12-week survivors only. The analysis will include separate comparisons of the effect of the BA-R intervention vs usual care control on each of the blinded outcomes in Table 4. These analyses will estimate the average treatment effect, i.e. the difference in the mean 12-week outcome comparing the BA-R intervention to the usual care control, using the precise locally efficient augmented simple estimator (PLEASE) described in Colantuoni and Rosenblum[REF: 135]. This method for estimating the average

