treatment effect is similar to the analysis of covariance (ANCOVA) approach in that it incorporates the baseline outcome (if measured) which, if correlated with the 12-week outcome, can improve the precision of the estimated average treatment effect [Ref 134]. This method also accounts for more general patient drop-out models than the ANCOVA approach. Specifically, the ANCOVA approach is valid under completely at random drop-out, whereas the PLEASE is valid under missing at random drop-out, i.e. when patient drop-out differs by treatment group or across levels of the baseline outcome or other measured variables at baseline. The PLEASE requires a priori specification of three models: an outcome regression model (fit separately for each treatment group) that will include age, gender and the baseline outcome (if measured), a propensity score model that will include age, gender and the baseline outcome (if measured) and a drop-out model (fit separately for each treatment group) that will include age, gender, and the outcomes measured at baseline (HADS, Brief Cope, CD RISC, BADS). As exploratory analyses, the 12-week outcomes (e.g. HADS scores) will be summarized (summary statistics including counts of missing values and histograms) and the correlation of the baseline (if appropriate) and 12-week outcomes will be computed, separately by treatment arm. Patient mortality, drop-out and missing data will be described for all variables, separately for treatment vs control groups. Patient characteristics will be compared between those with vs. without missing outcomes (due to drop-out and missing values).¹³⁶⁻¹³⁸

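### With 27 per group, SD 4.2, two-sided 5% alpha and 80% power, the unadjusted detectable HADS difference is 3.20 to 3.26 points, not the stated 3.1

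*Combined protocol and SAP*

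**What the plan says.** The Sample Size paragraph of section 7c gives the inputs in one sentence: "With 54 participants (27 in each group), assuming 5% alpha, 80% power and HAD SD of 4.2 points". From these it states that "we can detect a 3.1 point difference in HADS score between the 2 treatment groups", and adds of that figure: "which approximates HAD's 2.9 point minimum important difference (MID) in ARF survivors". It names no test, gives no sidedness and mentions no covariate adjustment.

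Three other places bear on the calculation:

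- Section 7c, Hypothesis 1b, sets the significance rule for the efficacy comparisons: "a 2-tailed p<0.05 is statistically significant".
- The same section plans a covariate-adjusted estimator (PLEASE) that uses age, gender and, where measured, the baseline outcome. On the correlation that governs the gain from adjustment, it says only that "the correlation of the baseline (if appropriate) and 12-week outcomes will be computed, separately by treatment arm".
- Section 4a (Overview of Research Methods) shows that 27 per group is a count of patients with 12-week data: "we will enroll up to 10 additional patients to obtain 12-week outcomes assessments on a total of 54 patients (27 in each group)".

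**The concern.** The paragraph gives everything needed for a two-sample comparison of means, so its result can be checked directly, and 3.1 does not come out. It is the only detectable-difference statement for the efficacy aim, and the plan uses it to place the trial close to the MID. A reader faced with a null HADS result, or planning the larger trial that this pilot is meant to inform, would take from it a somewhat more favourable picture than the inputs support.

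**Working it through.** **Inputs.** From the Sample Size paragraph: n = 27 per group, SD = 4.2, alpha = 0.05, power = 80%, stated detectable difference 3.1, MID 2.9. From Hypothesis 1b: two-tailed test.

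**Detectable difference, unadjusted.** The standard error of the difference is 4.2 × √(2/27) = 4.2 × 0.2722 = 1.143.

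- Normal approximation: (1.960 + 0.842) × 1.143 = **3.20**.
- t-test (noncentral t, 52 df, solved for 80% power): **3.26**.

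The plan's 3.1 is not reproduced. The gap is 0.10 to 0.16 points, or 3 to 5% of 3.1.

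**Power at the two differences of interest.** By the normal approximation, power = Φ(difference/1.143 − 1.960).

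| True difference | Difference / SE | Power, normal | Power, t |
|---|---|---|---|
| 3.1 | 2.712 | 77.4% | 75.9% |
| 2.9 (MID) | 2.537 | 71.8% | 70.2% |

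**Sample size that 3.1 would need.** n per group = 2 × (4.2 × 2.802/3.1)² = 28.8. That is 29 per group by the normal approximation and 30 by the t-test, so 58 or 60 patients with outcomes rather than 54.

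**How much of the shortfall at the MID is due to the slip.** For 3.1 to be right with 27 per group, the SD would have to be 4.2 × 3.1/3.202 = 4.07 (normal) or 4.2 × 3.1/3.263 = 3.99 (t). With either SD, by its own method, power at 2.9 is 74.6%. The slip therefore costs 74.6 − 71.8 = 2.8 percentage points (normal) or 74.6 − 70.2 = 4.4 (t). The remaining distance from 80% is already implied by 3.1 being larger than 2.9.

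**Other readings tried.**

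| Reading | Detectable difference, normal / t |
|---|---|
| One-sided 5% test | 2.84 / 2.88 |
| SD 4.15, the lowest value that rounds to 4.2 | 3.16 / 3.22 |
| 28 per group | 3.14 / 3.20 |
| 29 per group | 3.09 / 3.14 |

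The one-sided test overshoots in the other direction. The lowest SD still prints as 3.2. The larger groups contradict the stated 27. Drop-out does not help either: the 27 are already patients with outcomes, and fewer would make the figure worse.

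**Baseline adjustment.** As an assumption, let adjustment for baseline HADS multiply the variance by 1 − r², where r is the baseline to 12-week correlation. The detectable difference is then 3.202 × √(1 − r²) (normal) or 3.263 × √(1 − r²) (t).

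- It equals 3.1 at r = √(1 − (3.1/3.202)²) = 0.25 (normal) or 0.31 (t).
- It equals 2.9 at r = 0.42 or 0.46.
- At r = 0.5 it is 2.77 or 2.83.

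None of these correlations is in the documents.

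**The case against.** The best defence is the planned analysis. The sample-size sentence does not say that it is unadjusted, and the prespecified estimator uses baseline HADS. A correlation as modest as 0.25 to 0.31 would give 3.1, and 0.5 would take the detectable difference below the MID. This stands in part: the unadjusted power is not the power of the planned analysis, and the latter is not established in either direction. But the sentence claims no credit for adjustment and the documents give no planning correlation. The printed figure therefore cannot be derived from what is printed.

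A second defence is rounding. With an SD of 4.15 and a difference just under 3.15, power is 79.6% by the normal approximation (78.1% by t). That is close, but it needs both figures at the edge of their rounding and still falls short of 80%.

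A third is that nothing depends on the figure. The sample size comes from accrual, efficacy is secondary, and the plan claims only that 3.1 approximates the MID, not 80% power at 2.9. All of this is true. It limits the importance of the point, but it does not make the stated figure correct.

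**Conclusion.** The concern holds. On the stated inputs, with a two-sided test and no covariate adjustment, the detectable difference is 3.20 to 3.26 points. The stated 3.1 carries about 76 to 77% power and the 2.9-point MID about 70 to 72%. In each power range the lower value is the t-test and the higher the normal approximation. The result assumes equal groups with complete 12-week data and a common SD of exactly 4.2. The effect is small and leaves the sample size, the design and the primary feasibility outcome as they are. What is shown is that the stated figure does not follow from its inputs, not that the baseline-adjusted analysis is underpowered.

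**What to change.** Replace the figure in the Sample Size paragraph of section 7c in one of two ways.

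1. Report the unadjusted calculation, for example: with 27 per group, SD 4.2, two-sided 5% alpha and 80% power, the unadjusted detectable HADS difference is about 3.2 to 3.3 points, with about 70 to 72% power at the 2.9-point MID.
2. If 3.1 was meant to reflect the baseline-adjusted analysis, say so, state the assumed correlation between baseline and 12-week HADS with its source, and give the detectable difference that follows from it.

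Either is a change of one sentence. The first prints a slightly less favourable number. Neither needs more patients or alters the design or the primary outcome.

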Health Care Utilization and Estimated Costs	Admission to hospital, nursing & rehabilitation facilities; plus mental health & physical rehab utilization (8 min)			x
Survival status	Patient/Proxy (<1 min)			x
Coping Style	Brief Cope (28 items; 10 min)	x		x
Social Engagement	BADS (25 items; 5 min)	x		x
Resilience	CD RISC (25 items; 10 min)	x		x
Cognitive Function	MoCA-BLIND (8 questions; 5 min)			x
PTSD	IES-R (22 items; 6 min)			x

Abbreviations: HADS= Hospital Anxiety and Depression Scale, SCID-5= Structured Clinical Interview for DSM-5 (Mood Disorders Section only), AMPAC-CAT= Activity Measure for Post-Acute Care--Computer Adaptive Test, BADS= Behavioral Activation for Depression Scale, CD RISC= Connor-Davidson Resilience Scale

a: semi-structured interview

Brief Cope: Coping strategies will be assessed using the self-reported 28-item Brief Cope Scale.⁹⁴ The scale is a valid and reliable, used in medical populations, with strong measurement properties.^{94,120,122} It will assess active (e.g. problem solving) versus avoidant coping (e.g., behavioral disengagement, self-blame).

Behavioral Activation for Depression (BAD) Scale: This 25-point scale⁹⁵ assesses social engagement and other aspects of behavioral activation. We demonstrated BADS's validity in medical populations with depressive symptoms and its sensitivity to change with depression treatment.¹⁶

Connor-Davidson Resilience Scale (CD RISC): This 25-item scale⁹⁶ assesses resilience. It has been validated in a variety of patient populations and specifically used in research involving ARF survivors.^{102,105,106}

Adherence to the BA-R Intervention: will be evaluated as done in prior studies^{83,85} by: (1) measuring the number of phone attempts needed by the OT to reach the participant for each session, and (2) calculating the proportion of sessions fully completed (with sub-analysis for number partially completed).

Montreal Cognitive Assessment (MoCA) – BLIND: is a validated phone-based version of the original MoCA,¹²³ a rapid screening instrument for mild cognitive dysfunction. The MoCA - BLIND assesses different cognitive domains including attention and concentration, memory, language, conceptual thinking, calculation and orientation. It will take 5 minutes to administer the MoCA-BLIND.

Impact of Events Scale – Revised (IES-R): This is the most commonly used instrument for assessing PTSD symptoms in ARF survivors.¹⁰⁷ It has 22 items, is reliable and valid.¹²⁴

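### The survivors-only rule for Hypothesis 1b makes the survival comparison degenerate and drops admissions before death, which can distort the healthcare-use result in either direction

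*Combined protocol and SAP*

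**What the plan says.** The analysis text for Hypothesis 1b (Section 7c) gives its reason for the restriction first: "Patient mortality is expected to occur infrequently (see Sample Size above) and not to differ by treatment vs. control group". It concludes: "therefore, all analyses will be conducted for 12-week survivors only". The next sentence commits to "separate comparisons of the effect of the BA-R intervention vs usual care control on each of the blinded outcomes in Table 4".

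Two rows of Table 4 matter here, both collected at the end of the intervention:

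- Survival status, with source "Patient/Proxy (<1 min".
- Health care utilization and estimated costs, given as "Admission to hospital, nursing & rehabilitation facilities; plus mental health & physical rehab utilization (8 min". This row names no proxy.

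Section 4c leaves only the SCID interviewer unmasked, so both rows count as blinded outcomes. Lower healthcare use is a named part of Hypothesis 1b; survival is not. Later in the same analysis text the plan adds: "Patient mortality, drop-out and missing data will be described for all variables, separately for treatment vs control groups".

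The plan gives no rule for care used before death, no composite outcome that includes death, and no sensitivity analysis for the case where deaths differ by arm.

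**The concern.** The restriction and the list of comparisons do not fit together for two outcomes.

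Survival status compared among survivors can return only one answer, whatever happened in the trial.

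Facility admissions are different from HADS or EQ-5D-5L. A symptom score does not exist after death, so a survivor analysis of it is a recognised choice. An admission before death is an observed event in a randomised patient, and the rule removes it on the basis of something that happened after randomisation. Neither of the plan's other provisions puts it back. Describing mortality by arm counts the deaths but not the care that preceded them. The drop-out model in the PLEASE estimator reweights for missing outcomes within the analysis set, and patients who died are outside that set.

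At stake is the reading of the healthcare-use part of Hypothesis 1b, and the definition of that outcome carried into the larger trials that this pilot is meant to inform.

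**Working it through.** **The plan's own figures.** The plan gives no figure for the effect of the survivors-only rule. The nearest input is the group's prior study of more than 500 ARF survivors (Section 7c, Sample Size): "loss to follow-up was 2% with 7% mortality at 6 months". The allocation is 27 per arm.

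**Step 1: survival.** Among 12-week survivors the proportion alive is 100% in each arm. The difference is 0 with no variance.

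**Step 2: 12-week mortality (assumption).** At a constant hazard, 7% over 26 weeks becomes 1 − (1 − 0.07)^(12/26) = 0.033. If the deaths came early, the 12-week figure could approach 7%. I use 3.3% to 7%.

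**Step 3: expected deaths.** 54 × 0.033 = 1.8 and 54 × 0.07 = 3.8. With all 10 replacement patients (64 enrolled): 2.1 and 4.5.

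**Step 4: chance imbalance.** Take two independent binomial counts with n = 27 and the same true risk in both arms.

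| 12-week risk | P(unequal deaths) | P(gap ≥ 2) | P(gap ≥ 3) |
|---|---|---|---|
| 3.3% | 67% | 23% | 6% |
| 7% | 78% | 41% | 17% |

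So an expectation that deaths will not differ does not give equal observed counts.

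**Step 5: effect on mean use.** Let survivors use m on average in both arms, and let those who die use r × m before death. The all-randomised mean in an arm with d deaths is [(27 − d)m + d·r·m]/27, which differs from the survivor mean by d(r − 1)m/27. With deaths of 2 v 0, dropping decedents therefore changes the between-arm difference by 2(r − 1)/27 of the survivor mean. The values of r are assumptions.

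| r | Change hidden by the rule, in the arm with 2 deaths |
|---|---|
| 0.5 | −4% |
| 1 | 0% |
| 2 | +7% |
| 3 | +15% |
| 5 | +30% |

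A positive value means that the survivors-only analysis makes the arm with more deaths look better than it was. A negative value means the reverse.

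**Step 6: the same on a proportion.** Assume an admission risk near 30%, so that 8/27 = 29.6% are admitted in each arm, with 2 deaths in one arm and none in the other. The survivors-only proportion in the arm with deaths is:

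- both decedents admitted: 6/25 = 24.0%, a shift of −5.6 points;
- one admitted: 7/25 = 28.0%, a shift of −1.6 points;
- neither admitted: 8/25 = 32.0%, a shift of +2.4 points.

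For scale, the standard error of the difference at 30% with 27 per arm is √(2 × 0.3 × 0.7/27) = 12.5 points.

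**The case against.** The other side has several good points.

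- **Mortality is reported.** The plan describes deaths by arm, and Hypothesis 1b does not name survival. A formal test would add little: even 5 v 0 deaths gives Fisher p = 0.051. This stands. The survival half is a conflict of wording, and no mortality information is lost.
- **There is no demonstrated systematic bias.** A reader might infer that the rule favours whichever arm has more deaths, because that arm loses its heaviest users. The documents do not support this. They give no figure for decedents' use, and an early death shortens the time in which admissions can accrue, so the direction can reverse (Steps 5 and 6). The probabilities in Step 4 assume equal risk. If death also relates to use in the same way in both arms, chance gaps fall either way equally and the expected distortion of the contrast is zero. Systematic bias needs an effect of treatment on death or on who dies, and the plan expects none. This stands.
- **The worst case is uncommon and small.** Exactly 2 v 0 deaths, in either direction, has probability 2 × P(0) × P(2) = 2 × 0.405 × 0.165 = 13% at 3.3% and 2 × 0.141 × 0.280 = 8% at 7%. The largest shift in Step 6 is under half a standard error. Eligibility also excludes patients expected to survive less than 6 months or not discharged home. This stands.

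What does not follow is that the rule is sound for admissions. In any one trial with unequal deaths, the analyst could not tell which way the result had moved, because the data needed to tell would have been excluded.

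**Conclusion.** The point holds as a conflict in the text with a small, conditional consequence. Followed literally, the survival comparison is degenerate and admissions before death are dropped. The healthcare-use result can then be distorted in either direction if the number of deaths, or the care used by those who die, differs between arms.

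About 2 to 4 deaths are expected in 54 patients, and a chance gap of 2 or more arises in about 23% to 41% of trials. These figures rest on 12-week mortality of 3.3% to 7%, derived from the plan's 6-month figure, and on equal true risk in the two arms. The use ratios and the 30% admission risk are assumptions made only to show scale.

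The outcome is one of many secondary outcomes in a pilot whose primary outcome is feasibility. The point is worth correcting because the correction is cheap. It does not threaten the trial's main conclusions, and it is not evidence that the plan favours either arm.

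**What to change.** Revise the Hypothesis 1b analysis text as follows:

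1. Keep the survivors-only rule for patient-reported and performance outcomes, and label those results as survivor estimands.
2. Exempt survival status, and report it by arm in all randomised patients. No formal test is needed.
3. Compare facility admissions in all randomised patients up to death or week 12. Allow for follow-up cut short by death, either through time at risk or through a composite with death such as days alive and out of a facility. A plain count up to death is not enough, because an early death at home would score as no use.
4. State which rule applies to the outpatient services in the same Table 4 row.

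The sample size and design do not change. The cost is a short SAP edit and a few added proxy questions about admissions for patients who die. Those questions are a small addition to data collection, because Table 4 names a proxy for survival status only.
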